2.2.4 Non-Clinical Implementation Endpoints

- Adoption and Accessibility*
 - Intervention uptake and completion rates by participant demographics, intervention format, site characteristics, and interventionist background
 - Client Satisfaction Questionnaire (CSQ)-8 scale scores and intervention satisfaction rates
 - *Satisfaction* is defined a priori by achieving standardized scores of 80 percent or greater on the CSQ-8 scale.^[74]

*The following implementation measures are approved as an exempt component of this research: interventionist knowledge, self-efficacy, and skills pre- and post-training, by format, site, and timepoint

- Maintenance
 - Structured qualitative interview of individuals responsible for conducting the IMPACT intervention at each site
 - Coding of a select subset of participant and staff qualitative interview transcripts to identify themes related to intervention implementation and dissemination
 - Incremental cost-effectiveness of IMPACT versus eSOC estimated using the Cost Effectiveness of Preventing AIDS Complications for Adolescents and Young Adults (CEPAC-AYA) model

3. Study Design

We will use the RE-AIM Framework to inform the design, implementation, and evaluation of the IMPACT intervention to reduce stimulant use and concurrent HIV sexual transmission risk. Following best practices described in the Expert Recommendations for Implementing Change (ERIC) framework,^[17] we will use a multifaceted training and implementation strategy for the Project IMPACT intervention across sites and formats (see details below). We will then enroll approximately 450 YGBSMM who report stimulant use in the context of CAS, who will be randomized using a 2:1 allocation ratio to either the IMPACT intervention or an eSOC control. Allowing for drop out prior to randomization, we aim to randomize 360 YGBSMM. To ensure geographic variability in our sample, we will enroll nationally. Those physically located near a participate in-person, while those not located near an ATN SC will participate virtually (i.e., online assessments and video-based counseling). We anticipate that about 50 percent of the randomized sample will participate virtually (n=180) and 50 percent inperson (n=180), and randomization will be stratified by site and format; the study is well-powered to detect differences in intervention effectiveness by format.

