3.1 Study Design Rationale

While attentive to the need for exportable, generalizable, brief interventions, it must be acknowledged that stimulant use is a highly complex and, generally, treatment-refractory problem. Hence, this study will evaluate an intervention approach that involves BA to re-engage YGBSMM in pleasurable non-drug use activities that will serve as a natural reinforcement for functional behavior, improve depressed mood when not on stimulants by experiencing an increase in pleasure, and decrease overall distress so that YGBSMM who use stimulants can better benefit from HIV RR counseling. Prior studies demonstrated that a 10-session intervention is acceptable and necessary for treatment and is a typical minimum length for CBT interventions for depression.

We also considered providing additional substance use treatment as part of the eSOC condition, but since there is no demonstrated efficacious intervention for stimulant use, we will not be withholding evidence-based treatment. Moreover, because we aim to assess effectiveness across multiple sites, we determined that allowing each site to determine its own SOC would be most appropriate and informative. Notably, we will document SOC at each site, tracking any changes over the study period.

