5.6 Randomization and Stratification

Randomization of participants to study arms will be performed through the EDC system's enrollment module. The study arm assignments will be generated by the statistician at the SDMC. The SC Research Coordinator or designee will complete an eCRF in the EDC system to verify participant eligibility. Upon completion of the randomization, relevant SC staff will receive immediate notification of the study arm assignment on the randomization screen in the EDC system, followed by email notification. The relevant SC staff will maintain records of the participant's study arm assignment in accordance with the ATN MOGO.

Participants will be allocated with a 2:1 representation to the two arms, with two-thirds randomized to the IMPACT intervention and one-third to eSOC group. Block randomization will be stratified by SC and intervention format (online vs. in-person) to ensure balanced representation in the two arms. This allocation ratio was chosen to ensure sufficient power to examine whether there are differences in intervention efficacy by delivery format. Participants will be randomized after completing the Enrollment Visit and the first two RR sessions.

A randomization assignment, once issued, will not be re-allocated. Details of the randomization process are described in the study-specific Randomization Plan.

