14.3.3 Analysis of Primary Endpoint

Estimands

The primary analysis of the primary endpoint will compare the rate of distinct acts of CAS over the course of follow-up between the IMPACT intervention arm and the eSOC comparison arm.

For this endpoint, the primary estimand is defined by the following attributes:

- **Intervention condition:** IMPACT intervention versus eSOC including the effects of intervention discontinuation and intake of additional interventions/therapies.
- **Population:** Cisgender YGBSMM as defined by the inclusion criteria to reflect the key population.
- Variable: Number of distinct acts of CAS without the use of a condom or without the protection of prevention-effective PrEP (for participants NLWHIV) or viral suppression (for participants LWHIV) over the course of follow-up.
- Intercurrent events: The following intercurrent events are anticipated:

- Discontinuation of intervention due to any reason
 - Handling strategy: treatment policy (captured through the intervention condition definition)
- Intake of additional interventions/therapies
 - Handling strategy: treatment policy (captured through the intervention condition definition)

Further intercurrent events are not anticipated at this time.

• **Population-level summary:** Rate ratio between intervention conditions

Analysis Models

For the primary endpoint, a marginal Poisson model will be used, with logarithmic link function, common intercept, linear fixed effect for intervention, and accounting for the length of the reporting period for each observation. A Generalized Estimating Equations (GEE) approach will be used to fit the model, assuming an unstructured working correlation structure. Given the possibility of missing data from participants who discontinue the study prior to the Month 12 visit, inverse probability weighting will be incorporated into the modeling procedure; more details will be described in the SAP. Substitute model specifications to be used in the event the primary model does not converge will be described in the SAP.

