Least squares means will be used to estimate intervention-specific rates; the rate point estimates and standard errors will be reported. The intervention comparison will use the rate ratio comparing IMPACT to eSOC, which will be estimated along with its 95 percent CI from the model. The primary hypotheses will be tested via the Type 3 likelihood ratio chi-square test of the intervention fixed effect. The test statistic value and p-value will be reported.

Supplemental and Sensitivity Analyses

Primary model estimates and results will be accompanied by tabulated summary statistics of the endpoint data by intervention and visit. The primary model will also be used to assess the treatment effect at the Month 4 and Month 8 time points by incorporating a covariate for time point using appropriate contrasts.

Additional models that add a linear effect for a baseline/demographic factor as well as an (intervention * factor) interaction term will be used to assess the effect of intervention by factor. The factors that will be investigated (in separate models) will include geography, HIV status, and race/ethnicity.

Sensitivity analyses will also be performed for the primary endpoint. The SAP will describe the analyses in more detail.

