14.3.4 Analysis of Secondary Endpoints

The primary analysis of the key secondary endpoint will compare the rate of stimulant use over the course of follow-up between the IMPACT intervention arm and the eSOC comparison arm.

For this endpoint, the primary estimand is defined by the following attributes:

• **Intervention condition:** IMPACT intervention vs. eSOC including the effects of intervention discontinuation and intake of additional interventions/therapies.

- **Population:** Cisgender YGBSMM as defined by the inclusion criteria to reflect the key population.
- Variable: Number of reported uses of stimulants over the course of follow-up.
- Intercurrent events: The following intercurrent events are anticipated:
 - Discontinuation of intervention due to any reason
 - Handling strategy: treatment policy (captured through the intervention condition definition)
 - Intake of additional interventions/therapies
 - Handling strategy: treatment policy (captured through the intervention condition definition)

Further intercurrent events are not anticipated at this time.

Population-level summary. Rate ratio between intervention conditions.

The analysis of the key secondary endpoint will follow the procedures outlined for the primary endpoint.

Secondary endpoints. For the secondary endpoints assessing effectiveness by intervention format, Poisson models will be fit. Additional models that add a linear effect for intervention format as well as an (intervention * intervention format) interaction term may be used to assess the effect of intervention by format.

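### Randomisation is stratified by SC and delivery format, but the stated primary model carries neither factor; if they predict the count, a robust-variance confidence interval is conservative and a little power is lost

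*Protocol*

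**What the plan says.** Section 5.6 of the protocol states: "Block randomization will be stratified by SC and intervention format (online vs. in-person) to ensure balanced representation in the two arms". Section 3 (Study Design) says the same: "randomization will be stratified by site and format".

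Section 14.3.3 gives the terms of the primary model: a marginal Poisson model "with logarithmic link function, common intercept, linear fixed effect for intervention, and accounting for the length of the reporting period for each observation". On estimation it says: "A Generalized Estimating Equations (GEE) approach will be used to fit the model, assuming an unstructured working correlation structure". Inverse probability weights are added for dropout. The IMPACT to eSOC rate ratio is the reported comparison, "which will be estimated along with its 95 percent CI from the model", and the hypothesis test is a Type 3 likelihood ratio chi-square test of the intervention effect. Section 14.3.4 sends the key secondary endpoint through the same procedure.

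SC appears in no model of the two effectiveness endpoints. Format appears only in the secondary analyses, and there as an option: "Additional models that add a linear effect for intervention format as well as an (intervention * intervention format) interaction term may be used". The supplementary factor models in 14.3.3 cover geography, HIV status and race/ethnicity.

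**The concern.** Blocking within strata holds the allocation close to 2:1 in every SC and format. Differences between strata in the underlying count then largely cancel out of the arm comparison. A model with one intercept does not know this. Its residuals still contain the stratum differences, and a robust variance built from those residuals counts them as noise. The standard error is then larger than the true sampling variability of the estimate, and the balance that the design paid for is not used.

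At stake is efficiency and an accurate interval on the two main effectiveness analyses. The size depends on how strongly SC and format predict the count. The protocol gives one reason to expect some SC effect: on standard of care, Section 3.1 says that "allowing each site to determine its own SOC would be most appropriate". This is a separate matter from adjusting for baseline CAS.

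**Working it through.** **The plan's own figures.** Section 14.2 gives 291 completers (194 IMPACT, 97 eSOC), 90 percent power, alpha 0.05, a 20 percent reduction, and 360 randomised for 20 percent attrition. The 2:1 splits agree (194/97 = 240/120 = 2). The attrition step gives 291/0.8 = 364 against 360 stated, and 360 × 0.8 = 288. The 291 cannot be rebuilt forwards, because no control rate, SD or overdispersion is given. Solving backwards, and taking the 90 percent as the power of the arm comparison:

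- SE needed = |ln 0.8| / (1.960 + 1.2816) = 0.2231 / 3.2415 = 0.0688
- √(1/97 + 1/194) = 0.1244
- implied coefficient of variation (CV) of a participant's total = 0.0688 / 0.1244 ≈ 0.554

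**Effect of omitting the strata.** Let R² be the share of between-person variance explained by SC and format. The protocol does not give it; I take 0 to 20 percent. Under stratified blocks the true SE is √(1 − R²) times the robust SE of the unadjusted model. Hence:

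- width of the 95 percent CI relative to the correct width = 1/√(1 − R²)
- size of a robust Wald test = 2Φ(−1.96/√(1 − R²))
- power without strata = Φ(1.2816/√(1 − R²))
- power with strata = Φ(3.2415/√(1 − R²) − 1.96)

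| Assumed R² | CI too wide by | Size, robust Wald | Power without strata | Power with strata | Gain (points) |
|---|---|---|---|---|---|
| 0% | 0% | 5.0% | 90.0% | 90.0% | 0 |
| 5% | 2.6% | 4.4% | 90.6% | 91.4% | 0.8 |
| 10% | 5.4% | 3.9% | 91.2% | 92.7% | 1.5 |
| 20% | 11.8% | 2.8% | 92.4% | 95.2% | 2.8 |

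The gains are differences of the rounded powers. For R² = 20 percent: 1/√0.8 = 1.118; 2Φ(−2.191) = 0.028; Φ(1.433) = 0.924; Φ(1.664) = 0.952.

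**Simulation check.** Assumptions: ten equal SC × format cells, 2:1 blocks of six, 288 analysed, gamma-Poisson 12-month totals with mean 18, complete data, no weighting, sandwich SE, 4,000 null and 2,000 alternative runs per setting. The adjusted model had one term per cell. At the implied CV:

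| Assumed R² | Size without / with strata | Power without / with strata |
|---|---|---|
| 0% | 0.052 / 0.054 | 0.877 / 0.875 |
| 5% | 0.052 / 0.057 | 0.904 / 0.909 |
| 10% | 0.041 / 0.050 | 0.902 / 0.917 |
| 20% | 0.030 / 0.050 | 0.905 / 0.945 |

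Under the null, the mean model SE against the true SE of the unadjusted estimate was 0.0690 against 0.0649 at 10 percent and 0.0689 against 0.0617 at 20 percent. The ratios, 1.06 and 1.12, are close to the formula's 1.054 and 1.118. At R² = 5 percent the predicted fall in size to 4.4 percent does not show.

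**Estimand.** With a true rate ratio of 0.80 the mean estimate was about 0.80 with and without strata, as expected for a log link, under which the rate ratio is collapsible over strata.

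**If counts vary more than the sample size implies.** At an assumed CV of 1.0 and R² = 20 percent, simulated power was 0.436 without and 0.534 with stratum terms.

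**The case against.** The strongest reply is that little is lost. On the figures above, the unadjusted analysis keeps at least its nominal 90 percent power, its error is in the safe direction, and at small R² the two models are practically the same. That stands, and it makes this a point of efficiency.

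Four stronger readings are tempting, and the documents do not support them.

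- *The 5 percent test runs below 5 percent.* This would follow for a robust Wald or score test. Section 14.3.3 names a Type 3 likelihood ratio test and no robust variance. Its size depends on implementation; with a naive Poisson likelihood, overdispersion would push the error the other way.
- *SC and format are known to be prognostic.* Section 3.1 shows that standard of care may differ by site, not that CAS counts do. Sections 7.2.3 and 8.2 describe different specimen handling by format and say nothing on recruitment; 5.2 describes one centralised pre-screener. Both arms receive the same two RR sessions. R² may be near zero.
- *Adjustment buys about five points at R² = 20 percent.* That sets 95.2 against the nominal 90. The unadjusted test itself rises to 92.4, so the formula gives 2.8.
- *There are ten clean strata.* Section 6.2 has virtual delivery provided centrally from two institutions, while 5.2 forwards candidates to an SC. SC and format may partly overlap, and the Randomization Plan is not shown.

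It can also be said that the SAP may settle the matter. Section 14.3.3 does leave some things to it, for example: "Substitute model specifications to be used in the event the primary model does not converge will be described in the SAP". Weighting details and sensitivity analyses are deferred as well. The terms of the primary model are not deferred; the protocol states them.

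**Conclusion.** The point holds as a mismatch between design and analysis that the protocol itself states, for the primary and the key secondary endpoint. Its consequence is conditional: if SC or format predicts the count, a robust-variance interval from the stated model is conservative, by up to about 12 percent of its width over the assumed range, with up to about 3 power points forgone. With no prognostic strata nothing is lost. The omission does not raise the false-positive rate and does not alter the estimand, so the unadjusted analysis is inefficient and not invalid.

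The textual mismatch is certain. The size is not: it rests on an assumed R², robust-variance inference, complete data and a 90 percent starting power. The change is worth making because it is cheap and aligns the analysis with the randomisation, not because the trial is at risk without it.

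**What to change.** In 14.3.3, replace the single-intercept, intervention-only specification with: *an intercept, fixed effects for the randomisation strata (SC and intervention format, as actually used in the Randomization Plan, with a pre-specified pooling rule for sparse or overlapping strata), and intervention*, leaving the allowance for reporting-period length as it is. Apply the same model to the key secondary endpoint in 14.3.4. Keep the unadjusted model as a sensitivity analysis.

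Cost: a few extra parameters (five if SC and format enter as main effects, 4 + 1) on roughly 290 to 360 participants, and no new data. Section 14 asks for a protocol amendment when the analysis methodology of a primary endpoint is redefined. If the change counts as major in that sense, SAP wording alone will not do; if it counts as minor, it should be described and justified in the SAP.

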14.3.4 Analysis of Secondary Endpoints

The primary analysis of the key secondary endpoint will compare the rate of stimulant use over the course of follow-up between the IMPACT intervention arm and the eSOC comparison arm.

For this endpoint, the primary estimand is defined by the following attributes:

• **Intervention condition:** IMPACT intervention vs. eSOC including the effects of intervention discontinuation and intake of additional interventions/therapies.

- **Population:** Cisgender YGBSMM as defined by the inclusion criteria to reflect the key population.
- Variable: Number of reported uses of stimulants over the course of follow-up.
- Intercurrent events: The following intercurrent events are anticipated:
 - Discontinuation of intervention due to any reason
 - Handling strategy: treatment policy (captured through the intervention condition definition)
 - Intake of additional interventions/therapies
 - Handling strategy: treatment policy (captured through the intervention condition definition)

Further intercurrent events are not anticipated at this time.

Population-level summary. Rate ratio between intervention conditions.

The analysis of the key secondary endpoint will follow the procedures outlined for the primary endpoint.

Secondary endpoints. For the secondary endpoints assessing effectiveness by intervention format, Poisson models will be fit. Additional models that add a linear effect for intervention format as well as an (intervention * intervention format) interaction term may be used to assess the effect of intervention by format.

14.3.5 Analysis of Non-Clinical Implementation Endpoints

Adoption and accessibility. Intervention uptake and completion rates will be summarized by intervention format (in-person vs. virtual), site characteristics (e.g., health center, academic research center, community-based organization), and interventionist background (e.g., specialized mental health training).

Study completion and early discontinuation will be summarized by intervention and baseline participant characteristics (e.g., age, stimulant use patterns, sexual behaviors, HIV serostatus).

Implementation. Fidelity checklist scores will be summarized for subjects on the intervention arm by format, site, and time, and compared using t-tests to identify any differences by format, site, and time (months since study initiation).

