	 Access to a computer/smartphone/tablet that can use video chat (e.g., Zoom or Google Meet); Provide a mailing address where they can receive a package; Access to stable internet that they can use for more than 2 hours at a time; Have a private place (where no one else can see or hear) where they can complete visits online; and Reside within the continental United States (U.S.).
Main Criteria for Exclusion	 Unable to provide informed consent due to severe mental or physical illness; Concurrent enrollment in another HIV prevention or treatment study (enrollment in a substance treatment program is acceptable); Non–English-speaking; Is currently incarcerated or pending incarceration; or Any other medical condition, medical/behavioral intervention, or other condition that, in the opinion of the SC Project Lead or designee, could interfere with the safety of participants or staff, adherence to study procedures, or compromise interpretation of study results.
Clinical Centers	Five SCs in the U.S. will participate in this study. Participants may also participate virtually through centralized administration of online assessments and video-based intervention sessions.
Study Duration	Estimated duration: 5 years
Length of Participation	Total participant duration: Approximately 12 months

Study Intervention	IMPACT is a status-neutral intervention that uses behavioral activation (BA)—an evidence-based, cognitive behavior therapy—as a treatment for stimulant use and sexual risk reduction (RR) counseling for YGBSMM.
	The IMPACT intervention includes 10 sessions: 2 intervention sessions of HIV RR, 1 session focused on orienting and rationale of BA, 6 sessions integrating BA and RR—including pre-exposure prophylaxis (PrEP) or antiretroviral therapy (ART) and HIV care—and 1 final session on relapse prevention.
	The enhanced Standard of Care (eSOC) group includes two HIV RR intervention sessions.
Criteria for Evaluation	 Primary endpoint: Distinct acts of CAS defined as anal sex acts without the use of a condom or without the protection of prevention-effective PrEP (for participants not living with HIV [NLWHIV]) or viral suppression (for participants living with HIV [LWHIV]) over the course of study follow-up
	 Key secondary endpoint: Stimulant use over the course of study follow-up (based on urine drug testing via Point-of-Care Testing [POCT] and/or self-report)

PROTOCOL SCHEMA

Figure 1 Flow Diagram of Study

Version 3.0 Version Date: 03-October-2024

1. Introduction

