6.2 Study Intervention Administration

The IMPACT arm consists of 10 sessions (approximately 50 minutes each) delivered over the course of approximately 10 weeks. The eSOC arm consists of two RR intervention sessions described in Section 6.1.

A participant is not required to finish all intervention sessions to complete a follow-up visit; it is acceptable to miss sessions and continue with follow-up visits. However, once the Month 4 visit is conducted, no further intervention sessions can occur.

Following best practices described in the ERIC framework,^[17] a multifaceted training and implementation strategy for interventionists will be used for implementing the IMPACT intervention across sites and formats. A detailed description (including the Working Alliance Inventory-Therapist Report) of the intervention training and ongoing evaluation plan was acknowledged as an exempt sub study (ATN 170 Addendum: Interventionist Training and Evaluation, Study 11201) by Sterling IRB on August 8, 2023.

To enhance and maximize the adoption and accessibility of the IMPACT intervention, the intervention will be implemented in two separate formats: in-person at the selected ATN SCs and virtually, provided by the central research staff at Brown University and UCLA. This will allow for the intervention to be offered to a larger, broader, and more diverse population in terms of geography and physical ability status.

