6.3 Study Intervention Fidelity

Intervention fidelity monitoring will consider interventionist adherence and competence. A rating checklist, called a Fidelity Form, will be used that includes whether the specific components of the modules of treatment were, in fact, delivered. The rating checklist will be completed by the Central Coordinating Research Team after reviewing the audio-recorded sessions. Competence will be ensured by weekly clinical supervision using the audio-recorded sessions and rating checklists. At least 10 percent of the sessions, and at least one session per week per interventionist, will be reviewed for adherence and competence and will have the rating

checklist applied. Although following the manual is important, flexibility in the timing of interventions, content emphasis, and the order of topics is important to keeping the treatment relevant to participants.

Once per year—while the intervention is being implemented—the Protocol Team will conduct qualitative interviews with study interventionists, as well as at least one site administrator at each SC, to obtain input on (1) strengths and challenges in implementing the IMPACT intervention; (2) ways to improve training, implementation, and content of the intervention; and (3) strategies for broad dissemination following study completion, including funding sources and potential partners.

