14.2 Sample Size Considerations

Careful consideration was given to the effect size used in the power analysis and is estimated based on data from previous studies. In our pilot study, the mean difference in CAS acts between the intervention versus control arm at 6 months was 4.7 (>50% reduction). Although the pilot study had a large effect on reductions in sexual risk behaviors, effect sizes from small studies like the pilot study are less reliable and frequently inflated.^[70] Additionally, in the present study, the eSOC comparison group will be receiving two RR sessions and, as such, they will likely also decrease their engagement in CAS. Therefore, the study is powered to detect a 20 percent (or greater) reduction in the number of CAS acts between groups in the 12-month follow-up period, expecting both groups to show improvements from baseline. This decision will account for the fact that in clinical trials in general, and HIV behavioral trials in particular, when the control group receives any of the intervention content, it is more difficult to find a between-group difference^[71-73] as well as take into account the fact that the primary timeframe in the present study is 12 months instead of 6. Lastly, a 20 percent or greater reduction in the number of CAS acts has been previously described as a clinically meaningful change related to HIV sexual risk outcomes.

Moreover, to ensure sufficient power to assess whether intervention effectiveness differs between intervention delivery format (i.e., virtual vs. in-person) with a power of 90 percent, alpha level of 0.05, 291 participants will need to complete the proposed intervention in order to examine difference between IMPACT (n=194) and eSOC control (n=97). We plan to randomize 360 participants (n=240 in IMPACT and n=120 in eSOC) to account for 20 percent attrition at the month 12 visit.

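### The named t-tests for fidelity scores do not fit five sites or a month scale, and they ignore clustering by interventionist

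*Protocol*

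**What the plan says.** Section 14.3.5, under its Implementation heading, states the data and the method in one sentence. "Fidelity checklist scores will be summarized for subjects on the intervention arm by format, site, and time", and the scores will be "compared using t-tests to identify any differences by format, site, and time (months since study initiation"). It names no other test or model for these scores, and it does not say whether the unit is the session, the participant or the interventionist.

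Four other places determine what those t-tests would be applied to:

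- **Sites.** The Synopsis says: "Five SCs in the U.S. will participate in this study".
- **Format.** Section 6.2 says the intervention is delivered "in-person at the selected ATN SCs and virtually, provided by the central research staff at Brown University and UCLA".
- **Rating scheme.** Section 6.3 says: "At least 10 percent of the sessions, and at least one session per week per interventionist, will be reviewed for adherence and competence".
- **Volume.** Section 6.2 says: "The IMPACT arm consists of 10 sessions (approximately 50 minutes each) delivered over the course of approximately 10 weeks". Section 14.2 gives the randomized numbers as "n=240 in IMPACT and n=120 in eSOC".

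Section 14.3.1 sets a two-sided 5% level unless otherwise specified, and it leaves further description of the analyses to the SAP.

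**The concern.** There are two separate problems.

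**Fit of the test to the factors.** Format has two levels, and a two-sample t-test can compare them. Site has five levels if it means SC. Time is measured in months over a study estimated to last five years. One ordinary t-test gives neither a single answer to whether the five sites differ nor a trend over months. Analysts would have to run several pairwise tests or choose a split of calendar time. The protocol specifies neither.

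**Independence.** Each interventionist supplies many rated sessions, because at least one is rated every week. Scores from one interventionist will tend to resemble each other. The two formats are delivered by different teams, and so are the sites. Format and site therefore differ mainly between interventionists, which is the setting where ignoring clustering distorts a test most. Averaging scores to the participant would not solve this, because participants share interventionists.

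At stake is a conclusion that one format or site delivers the intervention less faithfully when the data show only ordinary variation between counselors. Section 1.2.1 defines the implementation part of RE-AIM as consistency of delivery across settings and over time, so such a conclusion could influence advice on dissemination.

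**Working it through.** The protocol states no power, sample size or error rate for the fidelity comparison, so there is no figure of its own to reproduce. The reference is the two-sided 5% level in Section 14.3.1.

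**Step 1: sites.** Five SCs give 5 × 4 / 2 = 10 pairs. Pairs share sites, so the tests are not independent. A simulation of five equal sites with independent scores (20,000 runs each) gave:

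| Scores per site | At least one of 10 pairwise t-tests significant | One-way F-test significant |
|---|---|---|
| 24 | 0.285 | 0.047 |
| 48 | 0.292 | 0.050 |

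A Bonferroni correction over 10 pairs would need 0.05 / 10 = 0.005 per test. One omnibus test holds the 5% level without it. Comparing months in pairs would be worse: 12 months alone give 12 × 11 / 2 = 66 pairs.

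**Step 2: number of rated sessions.** Ten percent of 240 × 10 sessions is 240. If only the 8 sessions after randomization count, 10% of 240 × 8 is 192. Both are minimum figures, because the weekly rule may add more.

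**Step 3: clustering.** The number of interventionists and the ICC of scores within interventionist are not in the protocol. I assume 3, 5 or 8 interventionists per format, equal numbers of sessions each (*m*), and an ICC of 0.05 to 0.30.

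- Design effect: DE = 1 + (*m* − 1) × ICC
- True error of a nominal 5% test: 2 × [1 − Φ(1.96 / √DE)]

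For 5 per format and 240 sessions, *m* = 240 / 10 = 24. At ICC 0.10, DE = 1 + 23 × 0.10 = 3.30. Then 1.96 / √3.30 = 1.08, and the error is 0.28. Simulation of the session-level format t-test (8,000 runs per setting) gave 0.29.

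| Total rated | Interventionists per format | *m* | ICC | DE | Error by formula | Error by simulation |
|---|---|---|---|---|---|---|
| 192 | 8 | 12 | 0.05 | 1.55 | 0.12 | 0.11 |
| 240 | 8 | 15 | 0.10 | 2.40 | 0.21 | 0.20 |
| 240 | 5 | 24 | 0.10 | 3.30 | 0.28 | 0.29 |
| 240 | 5 | 24 | 0.20 | 5.60 | 0.41 | 0.41 |
| 240 | 3 | 40 | 0.30 | 12.70 | 0.58 | 0.61 |

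The first and last rows are the extremes of the grid. With ICC 0 the simulated error was 0.047 to 0.054, so the excess comes from clustering alone.

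**Step 4: check of the remedy.** In the same simulations, a t-test on interventionist means had an error of 0.046 to 0.056 at every setting.

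**The case against.** The strongest defense is that this is an exploratory comparison whose detail belongs in the SAP. No hypothesis in Section 14.1, power statement or decision rule attaches to fidelity. Section 2.2.4 lists no fidelity score among the implementation endpoints. The opening of Section 14 lets the SAP describe minor changes. This settles the priority of the point: it is minor. It does not remove it, because the protocol itself names the test, and a SAP that only adds description would carry it forward.

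Some stronger readings are tempting, but the documents do not support them:

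- **A t-test cannot be used at all.** Pairwise t-tests, a split into two periods, or a t-test of a slope on months are all possible. The text states none of them. For format, the t-test is adequate in form.
- **Ten tests give a 40% false-positive risk.** That is 1 − 0.95^10 = 0.40, which needs independent tests. Pairs drawn from five shared sites are not independent, and 28–29% is the better figure. Even that assumes that every pair is tested and that site means SC, and Section 14.3.5 says neither.
- **Scores are also repeated within participant.** This is not established. Ten percent of 10 sessions is about one per participant. The weekly rule guarantees repetition within interventionist only.
- **Fidelity is a main result of the trial.** Sections 1.2.1 and 3 show interest in consistent delivery, but the endpoint list does not give fidelity that standing.

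It is also fair to object that the clustering figures depend on assumed inputs. They do, so they are given as a range. Every setting tried with a positive ICC exceeded 5%.

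**Conclusion.** The point holds as a wrongly stated method, at low priority. The named t-test suits format in form, gives no single test across five SCs, and gives no trend over months. Under a plain t-test, the rating scheme and the split of delivery teams lead to too many false differences by format and site.

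The size rests on stated conditions:

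- **Site:** about a 28–29% chance of at least one false difference, if all 10 pairs are tested, the sites are equal and scores are independent.
- **Format:** a true error of about 11% to 61% for a nominal 5% test, assuming 3 to 8 interventionists per format, equal workloads, an ICC of 0.05 to 0.30, and 192 to 240 rated sessions.

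A reader might infer that the trial's effectiveness findings are in doubt. They are not: the primary, key secondary and safety analyses do not use this comparison.

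**What to change.** In Section 14.3.5, replace the t-test wording with a linear mixed model for the fidelity score, specified as follows:

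- a random intercept for interventionist, with small-sample degrees of freedom;
- a fixed effect for format;
- one omnibus test for site;
- months since the study began as a continuous term.

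An analysis of interventionist-level means is a simple alternative for the format comparison.

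Two conditions should be written in. If virtual delivery is coded to a central team, format is determined by site and separate fixed effects for both cannot be estimated. Site should then be defined within format. A participant random effect should be added only if participants have more than one rated session.

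The cost in text is a sentence or two and one model. The statistical cost is wider intervals: in the middle case above, by a factor of about √3.30 = 1.8 before the small-sample correction. Where a site has only one or two interventionists, its effect may be poorly estimable or inseparable from the interventionist. Such sites should be reported descriptively.
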